Tumors were staged as per 8th edition of AJCC-TNM staging. Preoperative workup included contrast enhanced axial imaging (CECT – contrast enhanced computed tomography). In few cases with high risk features (residual disease on CT scan or late presentation), Positron Emission Tomography (PET) scan was added. Participants found fit for surgery and those with resectable disease on imaging were considered for the definite procedure. Laparoscopy was done preferably in those presenting beyond 4 weeks of index surgery or residual disease (local or nodal) on imaging to rule out metastasis. In absence of obvious distant metastasis (ascites, peritoneal nodules, mesenteric nodules, serosal nodules), inter-aortocaval (IAC) tissue was sent for evaluation of nodal metastasis. Once IAC node was found negative for deposits on frozen-section examination, radical re-resection was attempted. It included wedge resection of liver or Segment 4b/5 excision with regional lymphadenectomy. Extrahepatic bile duct excision was added in presence of positive cystic duct margin or direct invasion into the duct.

All available histopathology blocks and slides following the index cholecystectomy were re-reviewed by the pathologists at our institute. Tumor type, differentiation and primary T stage were documented for majority of cases. Interval between index cholecystectomy and date of re-operation was calculated for all the participants and divided into 3 groups: Early (<4weeks),

Intermediate (4-12 weeks) and Late (>12 weeks). Primary objective was to assess the effect of tumor characteristics and the time gap (between index surgery and re-resection) on overall survival following curative (R0/R1) resection.

Statistical Analysis:

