Continuous variables were presented in median (range) while categorical data was expressed in frequency (%). A variable was considered as normally distributed when the Z-score was within ± 3.29 ($n \geq 50$). To compare the means/medians between two groups, independent samples t-test/Mann Whitney U test was used. To test the association between categorical variables, Chi square tests or Fisher exact test was used. Event free survival was calculated for the patients using the Kaplan-Meier survival plots using Log rank test and Breslow test. Univariate and multivariate Cox regression analysis were used to identify the predictors of survival. Variables found significant in Univariate analysis were included for multivariate analysis. A two tailed p-value of < 0.05 was considered statistically significant. Statistical package for social sciences version-23 (SPSS-23, IBM, Chicago, USA) and MedCals software was used for data analysis.

RESULTS:

During the study period, 48 participants {11 (22.9%) in Group 'E', 31 (64.5%) in Group 'I' and 6 (12.5%) in Group 'L'} underwent re-resection with curative intent. The demographic profile (age and gender), co-morbidities, tumor characteristics, extent of resection, resection margin and nodal clearance were similar in the three groups (each $p > 0.05$). Median age of participants with IGBC was 55 years and 2.7 times more common among females.

Similarly, presence of residual disease, grades of the tumor, primary stage of the tumor following index cholecystectomy, final stage after curative resection, adjuvant therapy and associated morbidity were statistically equal among the groups (each $p > 0.05$). No post operative mortality was recorded. The most common complication in the postoperative period was surgical site infection (SSI), recorded in 8 patients. Three patients required postoperative percutaneous drainage for intra-abdominal collection. No patient required prolonged hospital stay or reoperation.

Overall Survival (OS) and Disease-free survival (DFS):

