On Univariate analysis of factors associated with significantly poor survival following curative resection were: presence of nodal metastasis, poor differentiation and lesions necessitating CBD excision. Other factors portending an unfavorable outcome included presence of residual disease, lympho-vascular invasion and delay in re-resection beyond 12 weeks, though the difference was not statistically significant. Primary tumor stage, resection margin and use of adjuvant therapy did not affect the overall survival (each $p > 0.05$). Residual disease was present in 20 out of 48 (41.6%) participants. The distribution of residual disease following re-resection, according to the index T-stage was (16% in T1, 29% in T2 and 72% in T3 tumors).

To further assess the predictors of survival among the participants, multivariate Cox regression analysis was used. Three variables (Node status, Grades and Extent of resection) which were significant on Univariate analysis were included in multivariate analysis. Results showed that disease grade was the only significant independent predictor of survival. Presence of positive

nodes ($p=0.052$) and the need for CBD excision (0.133) was associated with increased relative risk of disease related mortality, although the difference was not statistically significant.

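### Grade is singled out as the only independent predictor from a three-variable Cox model with at most 24 deaths and no hazard ratios, while nodes sit at p=0.052

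*Combined protocol and SAP*

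**What the plan says.** The Statistical Analysis section sets the selection rule, "Variables found significant in Univariate analysis were included for multivariate analysis", and the threshold, "A two tailed p-value of < 0.05 was considered statistically significant".

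The Survival Analysis section applies the rule: "Three variables (Node status, Grades and Extent of resection) which were significant on Univariate analysis were included in multivariate analysis". It then states that "disease grade was the only significant independent predictor of survival". The next sentence says that positive "nodes ($p=0.052$) and the need for CBD excision (0.133) was associated with increased relative risk of disease related mortality", and adds that neither result was statistically significant.

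The documents do not give the p-value for grade, any hazard ratio or interval, the coding of grade, or the number of patients and deaths in the model. On index histology, the Study Plan says: "Tumor type, differentiation and primary T stage were documented for majority of cases".

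**The concern.** The sentence ranks prognostic factors by which side of 0.05 each p-value falls on. One factor being significant and another not is not a test of whether their effects differ. With few deaths spread over three or more parameters, hazard ratios from ordinary Cox regression are unstable, and which variable crosses the threshold is partly chance. Choosing the variables by univariate significance adds optimism.

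The primary objective covers tumor characteristics as well as the time gap, and the timing comparisons were not significant (p=0.575 and p=0.581). Grade is the one factor reported as significant in the multivariable model, so readers are likely to carry it away.

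**Working it through.** There is no event count, sample size calculation or hazard ratio in the plan to reproduce, so the check works from what is reported.

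**Inputs.**
- Results: "48 participants {11 (22.9%) in Group 'E', 31 (64.5%) in Group 'I' and 6 (12.5%) in Group 'L", so n = 48.
- Overall survival section: mean follow-up 51.6 months, maximum 130.6, mean OS 91.75 months, and an OS curve that did not drop below 50%.
- Survival Analysis: p = 0.052 for nodes and 0.133 for CBD excision, which is taken here to be the extent-of-resection variable.

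**1. Upper bound on deaths.** Each death lowers a Kaplan-Meier curve by at least 1/n, so S ≤ 1 − d/n. With S ≥ 0.5 and n = 48, d ≤ 24. That is at most 24/3 = 8 deaths per parameter, or 24/4 = 6 if grade has three levels. The disease-free curve also stayed at or above 50%, so the bound is the same if the model counted recurrences.

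**2. Likely number of deaths (an inference).** Treat 91.75 as a mean restricted to 130.6 months and assume exponential survival:
- (1 − exp(−130.6λ))/λ = 91.75 gives λ = 0.00577 per month.
- Deaths = 0.00577 × 48 × 51.6 = 14.3, or 14.3/3 = 4.8 per parameter (3.6 with four parameters).

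For a range, the printed OS interval (8.32 to 75.44) excludes its own estimate, but 91.75 − 1.96 × 8.32 = 75.44. So 8.32 looks like a standard error, and the upper limit would be 91.75 + 1.96 × 8.32 = 108.06. Solving at 75.44 and 108.06 gives 23.1 and 7.4 deaths, or 7.7 and 2.5 per parameter. Weibull and cure models calibrated to the same summaries gave 14.1 to 14.5 expected deaths.

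**3. Screening.** The univariate text names nine factors: nodes, differentiation, CBD excision, residual disease, lympho-vascular invasion, delay, primary stage, margin and adjuvant therapy. That is 14.3/9 = 1.6 inferred deaths per candidate, and at most 24/9 = 2.7.

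**4. What p=0.052 and p=0.133 allow.** For a Wald p-value, |z| = 1.943 for nodes and 1.502 for CBD excision. The 95% limits are HR^(1 ± 1.96/|z|), with exponents −0.009 and 2.009 for nodes and −0.305 and 2.305 for CBD excision. The hazard ratios are not reported, so these are illustrations:

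| Assumed HR | Nodes 95% CI | CBD excision 95% CI |
|---|---|---|
| 2 | 0.99 to 4.0 | 0.81 to 4.9 |
| 3 | 0.99 to 9.1 | 0.72 to 12.6 |
| 4 | 0.99 to 16.2 | 0.66 to 24.4 |

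**5. Would grade differ from nodes?** Assume one parameter for grade, equal standard errors and uncorrelated estimates. The test of the difference is then (z_grade − 1.943)/√2.

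| Assumed grade p | z_grade | p for difference |
|---|---|---|
| 0.049 | 1.969 | 0.99 |
| 0.01 | 2.576 | 0.65 |
| 0.001 | 3.291 | 0.34 |
| 0.0001 | 3.891 | 0.17 |

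A difference at 0.05 needs z_grade = 1.943 + 1.96 × √2 = 4.715, which is p of about 2 × 10⁻⁶. Correlations from −0.3 to 0.3 move this from 3 × 10⁻⁷ to 2 × 10⁻⁵.

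**6. Simulation with equal true effects.** All effect sizes and prevalences here are assumed.
- 48 patients; prevalences 30%, 25% and 25%; true HR 2.5 for both nodes and grade and 1.5 for the third factor; about 14 to 17 deaths. Each of nodes and grade was significant in 37 to 43% of datasets. Grade significant with nodes not significant appeared in 21 to 25%.
- 12 to 16 deaths and the same HR for all three factors. Exactly one factor was significant in 44% of datasets at HR 2, 35% at HR 3 and 17% at HR 4.

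**The case against.** The strongest reply is that the statement is literally correct. At the stated two-sided 0.05, 0.052 and 0.133 are not significant. The text prints both p-values and says that nodes and CBD excision carried raised risk. This stands: the document does not claim that nodal disease has no independent effect, and a reader who infers that goes beyond it. What remains is that grade is still singled out with no effect size or comparison behind it.

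Four stronger readings are tempting, and the documents do not support them:

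- *Grade and nodes have been shown to be indistinguishable.* Grade's estimate is not reported. The comparison in step 5 assumes equal standard errors and a single grade parameter. The supportable statement is that no evidence of a difference is given.
- *There were 14 deaths.* No count is reported, and how follow-up was calculated is not stated. Only the bound of 24 follows directly from the reported curve.
- *The model dropped patients with missing grade.* The sentence on incomplete documentation concerns re-review of index blocks and slides. The database also held outside investigations and final histopathology. Exclusion is possible but unknown.
- *Grade is the headline conclusion.* The title question is the timing of re-resection. Grade belongs to the tumor-characteristics part of the primary objective.

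It is also fair to say that no separation or non-convergence is shown, so a penalised fit is one reasonable choice and not the only one.

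**Conclusion.** The concern holds in a limited form: singling out grade is not supported by what is reported. The firm part is at most 24 deaths, hence at most 8 per parameter, for variables screened by univariate significance. About 14 deaths, or 5 per parameter, is the likely figure if the restricted-mean and person-time assumptions hold (range about 7 to 23 deaths). Nodes miss the threshold by 0.017 on the z scale (1.960 − 1.943). The reported pattern is common by chance when the true effects are equal: about one dataset in four or five under the assumed HR of 2.5. The assumed hazard ratios and prevalences affect that frequency, but not the bound on deaths or the position of p=0.052.

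**What to change.** 1. Refit the same three-variable model with Firth-penalised Cox regression and profile-likelihood 95% CIs, at least as a sensitivity analysis. In simulation at about 15 deaths, with assumed hazard ratios and prevalences, the penalty cut the root mean squared error of the log hazard ratios from about 0.9–1.3 to about 0.6.
2. Report the patients and deaths in the model, how many patients lacked grade and how they were handled, the coding of grade, and HR, 95% CI and p for all three variables.
3. Replace the claim that grade alone predicts survival with an exploratory statement worded from the refitted estimates. Treat nodal status as inconclusive, not absent. Do not rank the factors unless a direct comparison of their effects supports it.

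The cost is a short re-analysis in software that offers Firth Cox, plus rewording. The conclusion becomes less clear-cut and p-values may cross 0.05 in either direction. Penalisation does not remove the bias from univariate screening, which should be stated as a limitation.
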